5.2.2. Day 3 and Day 7 Subject “Check-In”

Research staff will call all subjects on Days 3 and 7 to assess tolerability of the study drug, any potential AEs, and hospitalization history. Additionally, on Day 7, subjects will be asked to complete the PGIC and PGIS. If the subject is in the hospital on Days 3 and/or 7, research staff will visit the subject in person to complete the “check-in,” and collect an NP swab to assess the duration and magnitude of virus shedding. If research staff are unable to reach subjects on Days 3 and 7, those “check-in” visits will be considered missed visits. Research staff must document each attempt made to reach the subject in the research record.

5.2.3. Day 28 Subject Follow-Up

Twenty-eight days from the date of enrollment, research staff will call the subject by telephone to complete the *Follow-Up Assessment (F13)* form, PGIC, and PGIS. Contact will be attempted on four consecutive days (unless requested otherwise by the subject) with at least one of the calls occurring during non-working hours (i.e., evenings or weekends). Subjects may be categorized as “unavailable for follow-up” if: 1) there is a minimum of four failed contact attempts; 2) the provided contact numbers are non-functional; or 3) the subject requests no further contact from the study.

If the subject remains in the hospital, he/she will undergo an in-person interview to complete the required evaluations.

5.2.4. Medical Record Review

Research staff will review subjects' medical records on Day 7 and Day 28. The following records will be reviewed:

- Day 7: Medical records from the subject's enrollment ED visit.
- Day 28: Medical records from subsequent ED visits, outpatient visits, and hospitalizations that occurred since the ED enrollment visit through Day 28. If the subject reports visits to other medical facilities at the "check-in" visits, the Day 28 follow-up visit, or at any other time, those records will be obtained and included in the medical record review.

6. Study Drug Management

6.1. Study Drug Supply

Two types of study drug will be used in the Randomized Controlled Trial of Influenza Antivirals. Subjects will be randomized to one of the following treatments:

- Oseltamivir (oral); or
- Peramivir (IV).

JHH and MMC will purchase oseltamivir.

BioCryst Pharmaceuticals, Inc. will provide peramivir to JHH for this study. JHH will distribute peramivir to MMC with permission from BioCryst Pharmaceuticals, Inc.

6.2. Study Drug Formulation and Storage

Oseltamivir (Tamiflu)

For this study oseltamivir capsules of 30 mg and 75 mg doses will be used.

- 30 mg capsules (30 mg free base equivalent of the phosphate salt): light yellow hard gelatin capsules. "ROCHE" is printed in blue ink on the light yellow body and "30 mg" is printed in blue ink on the light yellow cap.
- 75 mg capsules (75 mg free base equivalent of the phosphate salt): grey/light yellow hard gelatin capsules. "ROCHE" is printed in blue ink on the grey body and "75 mg" is printed in blue ink on the light yellow cap.

Oseltamivir capsules should be stored at 25°C (77°F); excursions permitted to 15° to 30°C (59° to 86°F).

Peramivir (Rapivab)

Peramivir injection is a clear, colorless sterile, isotonic solution. Each single-use vial contains 200 mg per 20 mL (10 mg/mL) of peramivir in a clear glass vial. Peramivir injection is supplied in cartons containing three single-use vials.

Vials of peramivir injection should be stored in original cartons at 20° to 25°C (68° to 77°F). Excursions are permitted to 15° to 30°C (59° to 86°F).

6.3. Study Drug Dispensing and Administration

Oseltamivir will be prescribed and dispensed based on the subject's CrCl result obtained at screening. The first dose of oseltamivir will be administered in the ED. The remaining doses will be dispensed and given to the subject before being discharged from the ED (see section 5.1.4).

Peramivir will be prescribed and dispensed based on the subject's CrCl result obtained at screening. Peramivir is prescribed as a onetime dose to be administered in the ED. If the subject is admitted to the hospital from the ED, the inpatient treating provider may choose to continue administering IV peramivir (see section 5.1.4). Refer to the peramivir package insert for instructions on preparing peramivir for IV infusion.

6.4. Study Drug Labeling

The Pharmacist of Record (PoR) is responsible for ensuring that each container of study drug, dispensed to subjects, is labeled in accordance with federal, local, and institutional labeling requirements. The label must bear the statement, "Caution: New Drug--Limited by Federal (or United States) law to investigational use" per 21 CFR 312.6 (a).

6.5. Study Drug Accountability

The PoR at each site is responsible for ordering, receiving, storing, and dispensing study drug and will be required to maintain study drug accountability records. Study drug supply must be stored separately from other clinical drug supplies and/or hospital stock. At study end all unused and expired oseltamivir will be destroyed according to institutional policies; peramivir will be returned to JHH. Subjects will not return unused study drug (see the MOP).

6.6. Monitoring Subject Compliance to Study Drug

To assess subject adherence to oseltamivir, research staff will review the subject's daily diary each day. Subjects will report whether or not study drug for the previous day was taken. This information will be abstracted and entered on the *Medication Form (F24)*.

7. Adverse Event Management

The 21 CFR 312.32 (a) defines an AE (also referred to as an adverse experience) as any unfavorable and unintended sign (e.g., an abnormal laboratory finding), symptom, or disease temporally associated with the use of a drug, and does not imply any judgment about causality. An AE can arise with any use of the drug (e.g., off-label use, use in combination with another drug) and with any route of administration, formulation, or dose, including an overdose. The occurrence of an AE may come to the attention of research staff during or after the study procedures and interviews.

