2.3.3 Missing Data

We will first assess the extent and pattern of missing data for all outcomes. If data are missing for only a small proportion, or if the missing is likely to be at random, data analysis will be conducted using available observations.

If a substantial proportion of subjects have missing information, we will further explore the pattern of missing data, and assess whether missingness or loss to follow up is associated with subjects' characteristics, disease severity or any other factors.

2.4 *Statistical Methods*

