4. PROPOSED SUMMARY TABLES, GRAPHS AND LISTINGS

4.1 Mock Tables

Table 1. Subject Demographics

Characteristics	Site 1			Site 2			Total		
	Arm 1 (n=)	Arm 2 (n=)	Total (n=)	Arm 1 (n=)	Arm 2 (n=)	Total (n=)	Arm 1 (n=)	Arm 2 (n=)	Total (n=)
Age 65 or Greater									
Chronic Pulmonary									
Chronic Cardiovascular									
Chronic Renal									
Chronic Hepatic									
Chronic Hematologic									
Chronic Metabolic									
Chronic Neurologic									
Immunosuppression									
Pregnancy or Less than Two Weeks Postpartum									
Morbid Obesity									
Resides in Nursing Home									
Native American									

Study Arm:

Arm 1 = Oral antiviral treatment (Oseltamivir)
Arm 2 = IV antiviral treatment (Peramivir)

Table 2. Subject Symptom Onset and Baseline NEWS Score

N (%)	Site 1			Site 2			Total			Influenza Type	
	Arm 1 (n=)	Arm 2 (n=)	Total (n=)	Arm 1 (n=)	Arm 2 (n=)	Total (n=)	Arm 1 (n=)	Arm 2 (n=)	Total (n=)	A (n=)	B (n=)
Time of Symptom Onset at Enrollment											
Within 2 Days											
3 Days											
4 Days											
NEWS Score											
Median (Min—Max)											
0											
1-3											
4-6											
>6											

Table 3. Summary of Subject Status

N (%)	Site 1			Site 2			Total			Influenza Type	
	Arm 1 (n=)	Arm 2 (n=)	Total (n=)	Arm 1 (n=)	Arm 2 (n=)	Total (n=)	Arm 1 (n=)	Arm 2 (n=)	Total (n=)	A (n=)	B (n=)
Subjects Enrolled											
Subjects Completed Treatment (%) in the ED											
Subjects Completed Follow up											
Number of Doses (Median, Min—Max)		-	-		-	-		-	-	-	-
NEWS Score											
Percent Daily Dairies Completed											

Table 4. Summary of FLU-PRO Symptoms

Symptom Severity Score by Domain of Symptoms	Mean (Standard Deviation), Min-Max										
	Site 1			Site 2			Total			Influenza Type	
	Arm 1 (n=)	Arm 2 (n=)	Total (n=)	Arm 1 (n=)	Arm 2 (n=)	Total (n=)	Arm 1 (n=)	Arm 2 (n=)	Total (n=)	A (n=)	B (n=)
Nose											
Throat											
Eyes											
Chest/ Respiratory											
Gastrointestinal											
Body/ Systemic											
Total											

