5.1.4. Treatment Administration

Subjects will begin their treatment regimen in the ED as described below:

Oseltamivir

Subjects randomized to the oral treatment arm will receive oral oseltamivir. Oseltamivir will be dosed based on CrCl results, as described below.

CrCl Result	Dosage of Oral Oseltamivir	Frequency/Duration
>60 mL/min	75 mg	Twice daily (every 12 hours) for 5 days
>30 – 60 mL/min	30 mg	Twice daily (every 12 hours) for 5 days
>10 – 30 mL/min	30 mg	Once daily (every 24 hours) for 5 days

The first dose will be administered in the ED following randomization. The remaining doses will be taken on the subsequent four days, whether they are inpatient or outpatient, based on the screening CrCl results. If a dose is missed, subjects will be instructed to take the missed dose as soon as they remember, unless it is two hours or less before the next scheduled dose; in this case, subjects will be instructed to discard the missed dose, and continue to take the next dose at the usual time. Subjects will be instructed not to take two doses at a time to make up for a missed dose.

Peramivir

Subjects randomized to the IV treatment group will receive IV peramivir. Peramivir will be dosed based on CrCl results, as described below.

CrCl Result	Dosage of IV Peramivir	Frequency/Duration
≥50 mL/min	600 mg	One time
30 – 49 mL/min	200 mg	One time
10 – 29 mL/min	100 mg	One time

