5.1.5. Enrollment Completion

At the completion of all enrollment processes, subjects will be reminded that they need to complete a daily diary (to assess daily symptom severity, safety data, study drug adherence, as applicable, and provide a functional assessment) for 14 days between 3:00 PM – 11:59 PM local time. Subjects will be encouraged to complete the daily diary at the same time each day. Subjects will be reminded that research staff will be contacting them regarding daily diary entries and self-assessments, and at Days 3, 7, and 28 to collect follow-up information.

Subjects will also be asked to sign an authorization for release of health information which will allow research staff to obtain information on the subject's visits to other hospitals, should there be any subsequent medical encounters in the following 28 days.

Subjects who are discharged from the ED will be instructed to follow the ED standard discharge procedures.

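### On the twice-daily oseltamivir regimens, the daily yes/no adherence report in Protocol 6.6 does not fix the dose count planned in SAP Table 3

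*Combined protocol and SAP*

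**What the plan says.** Protocol 5.1.5 gives the daily diary several purposes, among them "study drug adherence, as applicable". Section 6.6 describes how this is done for oseltamivir: "Subjects will report whether or not study drug for the previous day was taken". Staff then transfer the answer to the Medication Form (F24).

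The dosing table in Protocol 5.1.4 has three oseltamivir rows. The two for creatinine clearance above 30 mL/min read "Twice daily (every 12 hours) for 5 days"; the row for >10 to 30 mL/min is once daily for 5 days. The first dose is given in the ED and the rest are placed on the four following days. For a missed dose remembered two hours or less before the next one is due, the section says "in this case, subjects will be instructed to discard the missed dose, and continue to take the next dose at the usual time".

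SAP 4.1, Table 3, contains the row "Number of Doses (Median, Min—Max". Only the Arm 1 (oral) cells are open; the other cells are dashed out. The row has no definition or source. The table's treatment-completion row is "Subjects Completed Treatment (%) in the ED", and a further row is "Percent Daily Dairies Completed".

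Other relevant text:
- Protocol 10.1 commits the CRFs to both the intended and the received total dosage, without naming a source for doses taken at home.
- Under Protocol 6.5, leftover drug is not collected.
- Under Protocol 5.2.1, a skipped diary day is lost.
- The Day 3 and Day 7 calls (5.2.2) cover tolerability, adverse events and hospitalization. Dose counting is not mentioned.

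**The concern.** The planned summary is in doses, but the collection method described is in days. On a twice-daily regimen a day can hold zero, one or two doses, and a two-way answer cannot separate three states. The protocol itself expects one-of-two days: the missed-dose rule in 5.1.4 produces them, and so can the instructions in 7.2.2 and 7.2.3 to hold the next dose after a rash or a change in behavior. For such a day, 6.6 does not say whether the answer is 'yes' or 'no'.

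No other source described in the documents recovers the number for a subject at home. In the mock tables this is the only row about the oral course after the ED dose, because the completion row stops at the ED. The pilot is meant to inform the design of later trials, and half-taken days are what a per-day item hides. The detail has to be captured when the diary is filled in, since there is no pill count to fall back on.

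**Working it through.** The documents give no figure for the number of doses, so there is no plan figure to reproduce. The check asks which dose totals are compatible with each pattern of daily answers.

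**Inputs.** Two doses a day for 5 days, or one dose a day for 5 days (Protocol 5.1.4). At least one dose on Day 1, because the first is given in the ED (5.1.4). One yes/no answer per day (6.6). All diaries are taken as completed.

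**Planned totals.** Twice daily: 2 × 5 = 10. Once daily: 1 × 5 = 5.

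**Reading A: 'yes' means at least one dose that day.** A 'yes' day holds 1 or 2 doses, and a 'no' day holds 0. Day 1 is always 'yes'. With y 'yes' days, the total lies between y and 2y.
- y = 5: 5 to 10 doses.
- There are 2^4 = 16 possible patterns. Since y is at least 1, all 16 fit more than one total.

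**Reading B: 'yes' means all of that day's doses.** A 'yes' day holds 2. A 'no' on Day 1 holds exactly 1 (the ED dose). A 'no' on Days 2 to 5 holds 0 or 1. Let d = 1 if Day 1 is 'no' and 0 otherwise, and let m be the number of 'no' answers on Days 2 to 5. The lowest total is 2(5 − m − d) + d, and the highest is that plus m.
- d = 0, m = 0 (five 'yes'): exactly 10.
- d = 1, m = 0: 2 × 4 + 1 = 9 exactly.
- d = 0, m = 1: 8 to 9.
- d = 1, m = 4 (five 'no'): 1 to 5.
- Of 2^5 = 32 patterns, only the two with m = 0 give a single total; 30 do not.

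**Once daily.** Each day holds 0 or 1 dose, so the count equals the number of 'yes' days under either reading.

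**Sensitivity to the calendar.** If the ED dose is late and only one dose falls on Day 1, two calendars are possible. Keeping literally to the four following days gives 1 + 4 × 2 = 9 doses. Giving all ten at 12-hour intervals runs into a sixth day: 1 + 4 × 2 + 1 = 10.

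| Calendar | All 'yes', reading A | All 'yes', reading B | Patterns fitting more than one total |
|---|---|---|---|
| 2+2+2+2+2 = 10 | 5 to 10 | 10 | A: 16 of 16; B: 30 of 32 |
| 1+2+2+2+2 = 9 | 5 to 9 | 9 | 15 of 16 under either |
| 1+2+2+2+2+1 = 10 | 6 to 10 | 10 | 30 of 32 under either |

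These are counts of possible answer patterns, not shares of subjects. The documents give no adherence rate from which to weight them.

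**The case against.** The strongest reply is that 6.6 is a one-sentence summary and not the wording of the item. Protocol 5.2.1 describes a diary section on medication adherence, 10.1 commits the CRFs to the dosage received, and Table 3 opens a dose row for the oral arm. Together these suggest that someone intended a dose-level record, and the forms may already hold one. This stands. A reader might infer that the dose count cannot be obtained at all, but the documents do not support that: the diary, F24 and MOP fields are not shown, and hospital records may supply inpatient doses. What remains is that the only at-home method described does not yield the planned figure.

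A second reply is that five 'yes' answers may simply mean a full course. Under reading B that is right. So one cannot say without qualification that a median of 10 is known only to lie between 5 and 10; that range belongs to reading A. Under reading B the uncertainty moves to the 'no' days.

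A reader might also infer that missed diaries bias the count downward, so that a fully adherent subject with k missing reports for Days 2 to 5 on the 2 × 5 calendar shows 10 − 2k doses. That needs a rule scoring a missing day as zero, and neither document states one. SAP 2.3.3, written for outcomes, says that under stated conditions "data analysis will be conducted using available observations"; it does not say how a sum over days treats a gap. Diary completeness is reported in Table 3, and staff call after a missed entry. The fair statement is that the rule is missing.

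**Conclusion.** The point holds in a limited form and is minor. For subjects on twice-daily oseltamivir, the item as Protocol 6.6 describes it does not determine the SAP Table 3 dose count under either reading of 'yes' or on any of the three calendars. Once-daily subjects are unaffected. Confidence is medium, because the forms have not been seen.

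A reader might infer that the trial's treatment outcome is compromised. It is not: SAP 2.3.1 lists receipt of the first oral dose in the ED, and enrolment and follow-up completion do not use the count. No test or comparison between arms is planned (SAP 2.4.2 and 3.4.1). The effect is confined to one descriptive adherence row.

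The number of subjects concerned cannot be fixed from the documents. For orientation, the planning figure of 58 discharged subjects in a routine season, based on data from one site, gives 58 / 2 = 29 oral subjects under 1:1 allocation. This is neither an upper nor a lower limit: the share on twice-daily dosing is not given, and admitted subjects who go home before the course ends may also take doses at home.

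**What to change.** - Change Protocol 6.6 so that the diary and F24 record the number of doses taken on the previous day: 0, 1 or 2.
- Footnote the Table 3 row as doses taken. Name the source (diary, or inpatient record while in hospital), and state that a missed diary day counts as unknown, not zero, with the number of such days shown.
- If only yes/no answers have been collected, report days with drug taken in place of doses, and say what 'yes' means.
- If the forms already record each dose, say so in 6.6 and in the footnote; nothing else is then needed beyond the missed-day rule.

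The cost is one slightly longer diary item, one form field, a sentence in 6.6 and a footnote. It needs no extra visit and no change to the dosing instructions in 5.1.4. Missed diary days will still leave gaps, but the gaps will be visible.

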7.1. General Management of Adverse Events

Acute management of any AE will be according to best clinical practices and the judgment of the site investigator. The relationship between the AE and the study intervention will be presumed related, unless a clearly recognized alternate etiology is identified. Alternative explanations for clinical or laboratory abnormalities must be sought prior to study drug discontinuation.

The following requirements for managing AEs during study participation should be followed, unless otherwise specified in section 7.2:

- Grades 1-4 AEs (not related to study drug):
Subjects may continue taking study drug per the discretion of the site investigator. The site investigator will monitor all AEs unrelated to study drug according to best clinical practices. Report the event as an AE, following instructions in section 8.1.1.
- Grades 1 and 2 AEs (related to study drug):
Subjects may continue taking study drug without alteration of the dosage or frequency, with the exceptions noted in section 7.2. The site investigator will monitor subjects according to best clinical practices. If the site investigator deems that the AE warrants study drug discontinuation, this should be communicated to the protocol team, prior to discontinuing the subject from study drug. Report the event as an AE, following instructions in section 8.1.1.
- Grades 3 and 4 AEs (related to study drug):
The site investigator will determine whether or not subjects may continue taking study drug based on his/her clinical judgment. The site investigator will closely monitor subjects according to best clinical practices until the AE resolves or stabilizes. If the site investigator deems that the AE warrants temporary or permanent study drug discontinuation, this should be communicated to the protocol team as soon as possible and preferably, prior to discontinuing the subject from study drug. Report the event as an AE, following instructions in section 8.1.1; and as an SAE if criteria are met, following instructions in section 8.1.2.

7.2. Protocol-Specific Adverse Event Management

7.2.1. Allergy/Hypersensitivity Reaction to Study Drug

If an allergic reaction occurs, instruct the subject to hold the next study drug dose and go to the ED immediately.

- Grades 1 and 2: Discontinue study drug immediately. The site investigator will closely monitor the subject according to best clinical practices until the AE resolves or stabilizes. Report the event as an AE, following instructions in section 8.1.1.

- Grades 3 and 4: Discontinue study drug immediately. The site investigator will closely monitor the subject according to best clinical practices until the AE resolves or stabilizes. Report the event as an AE and SAE, following instructions in sections 8.1.1 and 8.1.2.

7.2.2. Rash or Skin Reaction

If a rash or skin reaction occurs, instruct the subject to hold the next study drug dose and go to the ED immediately. Any rash or skin reaction that is assessed to be possibly, probably, or definitely related to study drug will be considered an allergy/hypersensitivity reaction to study drug.

- Grades 1 - 4 (not related): Subjects may continue taking study drug per the discretion of the site investigator. The site investigator will monitor all AEs unrelated to study drug according to best clinical practices. Report the event as an AE, following instructions in section 8.1.1.
- Grades 1 and 2 (related): Refer to section 7.2.1 for AE management instructions.
- Grades 3 and 4 (related): Refer to section 7.2.1 for AE management instructions.

7.2.3. Altered Mental Status

If a change in behavior occurs, such as confusion or hallucinations, instruct the subject to hold the next study drug dose and go to the ED immediately. Refer to section 7.1 for AE management instructions.

8. Safety Reporting

8.1. Documenting, Recording, and Reporting Adverse Events

At each follow-up contact with the subject (i.e., phone call follow-up for outpatient and in-person follow-up for inpatients), information regarding AEs and unanticipated problems will be elicited by appropriate questioning and will be documented and reported as outlined below.

8.1.1. Adverse Event

All AEs including local and systemic reactions not meeting the criteria for an SAE will be captured on the *Adverse Events (F20)* form. All AEs occurring while on study will be documented appropriately regardless of relationship.

Any medical condition that was present at the time that the subject was screened/enrolled will be considered a baseline event. It will not be considered an AE. However, if the event worsens at any time after study drug administration through completion of the study period (Day 28), the event will be reported as an AE.

All AEs will be graded for severity and a relationship to the study drug will be assigned.

Severity of all AEs will be assessed by a site investigator using the Division of AIDS (DAIDS) Table for Grading the Severity of Adult and Pediatric Adverse Events (Version 2.0, November 2014). The grading scale is as follows:

Mild (Grade 1): Mild symptoms causing no or minimal interference with usual social and functional activities with intervention not indicated

Moderate (Grade 2): Moderate symptoms causing greater than minimal interference with usual social and functional activities with intervention indicated

Severe (Grade 3): Severe symptoms causing inability to perform usual social and functional activities with intervention or hospitalization indicated

Potentially Life-Threatening (Grade 4): Potentially life-threatening symptoms causing inability to perform basic self-care functions with intervention indicated to prevent permanent impairment, persistent disability, or death

Death (Grade 5): Events resulting in death

Relationship to study drug or causality (likelihood that the event is related to the study drug) will be assessed for all AEs by the site investigator and the ISM. For the purposes of investigational new drug (IND) safety reporting, 'reasonable possibility' of relationship means there is evidence to suggest a causal relationship between the study drug and the AE. Such evidence includes temporal relationship between study drug administration and event, a known or suspected response pattern based on similar agents, and the likelihood (or lack thereof) of an alternative etiology. If a site investigator assesses an AE to be definitely, probably, or possibly related to study drug, the AE will be reported as related. If an AE can be clearly explained by another cause not related to the study drug, then the AE will be reported as not related and an alternative etiology will be documented.

Note: Causality assessment is based on available information at the time of the assessment of the event. The investigator and/or the ISM may revise the causality assessment as additional information becomes available.

